# 2 SYNOPSIS

Name of Sponsor:	Name of Finished Product:	Name of Active Ingredient:		
Cumberland Pharmaceuticals	Ifetroban Capsules	ifetroban		

# **Title of Study:**

A Phase 2 Multicenter, Double-blind, Randomized, Placebo-Controlled Trial to Evaluate Oral Ifetroban in Subjects with Symptomatic Aspirin Exacerbated Respiratory Disease (AERD)

# Study Centers (Planned): Eight | Phase of Development: II

**Expected Study Duration (per subject):** Screening period (3 weeks) + Treatment period (8 weeks) + Post-treatment period (2 weeks) = 13 weeks

# **Objectives:**

# **Primary Study Objective**

• Determine the efficacy of ifetroban compared to placebo to improve sino-nasal symptoms and quality of life (QoL) using the Sino-nasal Outcome Test (SNOT) - 22 score in symptomatic AERD subjects.

# **Secondary Study Objectives**

- Evaluate the effect of ifetroban on asthma symptoms by forced expiratory volume 1 (FEV1) compared to baseline.
- Assess nasal symptoms and QoL using the peak Nasal Inspiratory Flow Rate (PNIFR), University of Pennsylvania Smell Identification Test (UPSIT), fractional exhaled nitric oxide (FeNO), Asthma Control Questionnaire (ACQ) 7 and Total Nasal Symptom Score (TNSS)
- Determine whether ifetroban reduces the frequency and severity of asthma exacerbations and chronic sinusitis as well as the frequency of rescue medication and antibiotic use.
- Evaluate the pharmacodynamic effects of TPr blockade on eicosanoids and eosinophil count

**Methodology:** This is a multicenter, randomized, double-blind, placebo-controlled study to evaluate the effect of 200 mg of oral ifetroban administered once daily for eight weeks.

**Number of subjects (planned):** A total of 76 AERD subjects will be randomized: 38 ifetroban, 38 placebo

Name of Sponsor:	Name of Finished Product:	Name of Active Ingredient:		
Cumberland Pharmaceuticals	Ifetroban Capsules	ifetroban		

# Study Population – Main Selection Criteria

# **Inclusion criteria:**

- 1. History of physician-diagnosed asthma
- 2. History of nasal polyposis
- 3. History of at least two reactions to oral aspirin or other nonselective cyclooxygenase inhibitor with features of lower airway involvement (cough, chest tightness, wheezing, dyspnea) or one reaction that was life-threatening and required hospitalization, or a diagnosis of AERD by a physician-conducted challenge to aspirin in the last five years before starting treatment.
- 4. Stable asthma (post-bronchodilator FEV1 of  $\geq$  60%, no glucocorticoid burst for at least two weeks prior to starting treatment, no hospitalizations or emergency room visits for asthma at least three months prior to starting treatment and not on a dose  $\geq$ 1000 µg fluticasone or equivalent daily).
- 5.  $\geq$  18 years of age
- 6. Exhibit symptomatic AERD within three weeks of starting treatment by demonstrating a score of at least 20 on the Sino-nasal Outcome Test (SNOT) 22.

# **Exclusion criteria:**

- 1. Current smoking, defined as daily tobacco smoking in the last six months and at least one instance of tobacco smoking in the last three months.
- 2. Current pregnancy or breastfeeding
- 3. Use of oral or systemic steroids (e.g. prednisone or equivalent) > 20 mg daily in the last four weeks before starting treatment.
- 4. Daily use of long-acting antihistamines in the last two weeks before starting treatment.
- 5. Less than 12 months of allergy shots (maintenance dose of allergy shots are allowed if treatment duration exceeds 12 months).
- 6. Any use of nonsteroidal anti-inflammatory drugs (NSAIDs) or any drug that inhibits the cyclooxygenase enzyme in the last two weeks before starting treatment.
- 7. History of bleeding diathesis or use of anticoagulant or antiplatelet drugs in the last two weeks before starting treatment.
- 8. Any immunosuppressive treatment including but not limited to methotrexate, cyclosporine, mycophenolate, tacrolimus, gold, penicillamine, sulfasalazine, hydroxychloroquine, azathioprine and cyclophosphamide in the last two weeks before starting treatment (maintenance dose of allergy shots are allowed if treatment duration exceeds 12 months). Biologics/immunotherapies such as Xolair or Nucala are permitted if duration exceeds three months.
- 9. Endoscopic sinus surgery / polypectomy within the past three months
- 10. Previously treated in a clinical trial with ifetroban within the past three months.
- 11. Previously treated with other investigational drugs within eight weeks or five half-lives, whichever is longer, before screening
- 12. Conditions/concomitant disease which make them unevaluable for the efficacy endpoints

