# 7.4 Selection of Study Population

Study eligibility will be determined by the Investigator based on the inclusion and exclusion criteria below.

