#### 7.4.2 Exclusion Criteria

Individuals who meet any of these criteria are not eligible for enrollment as study subjects:

- 1. Current smoking, defined as daily tobacco smoking in the last six months and at least one instance of tobacco smoking in the last three months
- 2. Current pregnancy or breastfeeding
- 3. Use of oral or systemic steroids (e.g. prednisone or equivalent) > 20 mg daily in the last four weeks before starting treatment
- 4. Daily use of long-acting antihistamines in the last two weeks before starting treatment
- 5. Less than 12 months of allergy shots (maintenance dose of allergy shots are allowed if treatment duration exceeds 12 months). Less than 1 month of 5-lipoxygenase inhibitors (e.g. zileuton) and/or leukotriene receptor antagonists (e.g. montelukast).
- 6. Any use of nonsteroidal anti-inflammatory drugs (NSAIDs) or any drug that inhibits the cyclooxygenase enzyme in the last two weeks before starting treatment
- 7. History of bleeding diathesis or use of anticoagulant or antiplatelet drugs in the last 2 weeks before starting treatment
- 8. Any immunosuppressive treatment including but not limited to methotrexate, cyclosporine, mycophenolate, tacrolimus, gold, penicillamine, sulfasalazine, hydroxychloroquine, azathioprine and cyclophosphamide in the last two weeks before starting treatment (maintenance dose of allergy shots are allowed if treatment duration exceeds 12 months). Biologics/immunotherapies such as Xolair or Nucala are permitted if duration exceeds three months.
- 9. Endoscopic sinus surgery / polypectomy within the past three months
- 10. Previously treated in any clinical trial with ifetroban
- 11. Previously treated with other investigational drugs within eight weeks or five half-lives, whichever is longer, before screening
- 12. Conditions/concomitant disease which make the participant unevaluable for the efficacy endpoints

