#### 8 STUDY VISITS AND PROCEDURES

# 8.1 Overview – Schedule of Time and Events

This 13-Week study will consist of a three-week Screening Period (Week -3 to Week 0), an 8-week Treatment Period (Week 0 to Week 8) and a two-week Post-treatment Period (Week 8 to Week 10). The study visits occur on the planned dates relative to the first dose of IMP as scheduled. The visit schedule should be adhered to within the  $\pm$  5 day visit window.

If a subject is prematurely discontinued from treatment, all assessments planned at the End of Treatment visit should be performed. Prior to all screening assessments, after discussion of participation in the study, the written consent form must be signed and dated. Although the screening assessments for this study are grouped under the heading of a single visit in this protocol, it is possible for them to be performed over more than one site visit if necessary, as long as the three-week screening period relative to the first dose of IMP is respected. Subjects that fail screening for exclusion criteria, for example concomitant medications, acute illness (upper respiratory tract infection), required drug-specific discontinuation periods or laboratory tests, may be rescreened for study eligibility one additional time.

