# 8.1.1 Screening Period

The Screening Period is defined as the three-week period prior to Week 0 (IMP administration).

Before the initiation of study-specific screening assessments, the subject must be given a complete explanation of the purpose of the study and evaluations that will be made as part of the study. Subsequently, the subject must sign and receive a copy of an Informed Consent Form that was approved by the Institutional Review Board (IRB)/Independent Ethics Committee (IEC). Once informed consent has been obtained, the eligibility of the subject to participate in this study will be determined by the Investigator on the basis of the inclusion and exclusion criteria in Section 7.4. Screening Period assessments will also be performed to determine eligibility. Only eligible subjects will be randomized to receive IMP at Week 0.

Following a discussion of participation in the clinical study and signed informed consent obtained, the following procedures will be performed to determine the subject's eligibility for this study (Table 8–1) during the Screening Period (Week -3 to Week 0):

- Informed Consent
- Interview to collect subject medical history, including but not limited to, disease history (including asthma history, number of asthma exacerbations in the previous year, hypersensitivity to aspirin or other NSAIDs), surgical history (including the number and dates of previous nasal polypectomies), recently discontinued and concomitant medications (include all background therapy for AERD).
- Demographic data
- Administer SNOT-22.
- Perform spirometry to ensure the subject has stable asthma (FEV1 ≥ 60% of predicted normal and has not experienced any exacerbation requiring treatment with ≥ 1 systemic (oral or parenteral) steroid bursts for worsening asthma and/or hospitalization or an emergency/urgent medical care visit for worsening asthma in the previous three months or are on a dose of inhaled corticosteroids > 1000 µg fluticasone or equivalent daily).
- Obtain fasting blood samples for screening clinical laboratory determinations:
  - Hematology: To include hemoglobin, hematocrit, platelet count, total white blood cell count with five-part differential count, and total red blood cell count.

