  - Serum chemistry: To include creatinine, blood urea nitrogen, glucose, uric acid, total cholesterol, total protein, albumin, total bilirubin, alanine aminotransferase, aspartate aminotransferase, alkaline phosphatase, electrolytes (sodium, potassium, chloride), bicarbonate, and creatine phosphokinase.
  - o Prothrombin time (PT) and international normalized ratio (INR)
- Review entry criteria to assess eligibility with special attention to verify the following:
  - History of at least two reactions to oral aspirin or other nonselective cyclooxygenase inhibitor with features of lower airway involvement (cough, chest tightness, wheezing, dyspnea) or one reaction that was life-threatening and required

hospitalization, or diagnosis of AERD via a physician-conducted challenge to aspirin in the last five years before starting treatment

- O Use of oral or systemic steroids (e.g. prednisone or equivalent) > 20 mg daily in the last four weeks before starting treatment, daily use of long-acting antihistamines in the last two weeks before starting treatment. Subjects on 5-lipoxygenase inhibitors (e.g. zileuton) and/or leukotriene receptor antagonists (e.g. montelukast) must be on a stable dose for ≥ 30 days before starting treatment. No NSAID, anticoagulants and immunosuppressive medication use is allowed.
- o Presence of a score of at least 20 on the SNOT 22
- Perform physical examination including vital signs [blood pressure, heart rate, respiration rate, body temperature, weight (kg), height (cm)]
- Obtain pregnancy test if female of child-bearing potential (pre-menopausal female biologically capable of becoming pregnant). Confirm subject is protected by one of the following acceptable forms of effective contraception during the study:
  - Established use of oral, injected or implanted hormonal contraceptive
  - "Double barrier" methods (i.e., Double Intrauterine device with copper or intrauterine system with progestogen and barrier contraceptive [condom, diaphragm or cervical/vault caps] used with spermicide [foam, gel, film, cream or suppository])
  - Female sterilization (e.g., tubal occlusion, hysterectomy or bilateral salpingectomy)
  - Male sterilization with post-vasectomy documentation of the absence of sperm in the ejaculate; for female subjects enrolled in the study, the vasectomized male partner should be the sole partner for that subject

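### No entry criterion limits the screening platelet count, so a subject already below the mandatory-withdrawal level is not expressly barred from randomization and dosing

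*Protocol*

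**What the plan says.** **Entry criteria.** Exclusion 7 in the protocol synopsis reads "History of bleeding diathesis or use of anticoagulant or antiplatelet drugs in the last two weeks before starting treatment". Section 7.4.2 repeats it as "History of bleeding diathesis or use of anticoagulant or antiplatelet drugs in the last 2 weeks before starting treatment". Exclusion 12, the only catch-all, is confined to conditions that prevent evaluation of efficacy.

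**What decides eligibility.** Section 7.4 opens: "Study eligibility will be determined by the Investigator based on the inclusion and exclusion criteria below". Section 8.1.1 states that eligibility "will be determined by the Investigator on the basis of the inclusion and exclusion criteria in Section 7.4", and adds: "Screening Period assessments will also be performed to determine eligibility".

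**What is measured.** The screening blood samples in 8.1.1 include "Hematology: To include hemoglobin, hematocrit, platelet count, total white blood cell count with five-part differential count, and total red blood cell count". The same section then asks the site to "Review entry criteria to assess eligibility with special attention to verify the following". The items that follow are aspirin reactions, medications and the SNOT-22 score.

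**Withdrawal.** Section 9.1 lists events that make withdrawal from the study compulsory. Thrombocytopenia < 50 × 10⁹/L is one of them.

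**The concern.** The entry rule and the withdrawal rule do not match. The sponsor has already judged a count below 50 × 10⁹/L unacceptable for staying in the study, but nothing states that the same count bars the first dose.

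The gap touches the protocol's own safety reasoning. Section 5.4 reports that oral doses of at least 100 mg inhibit platelet aggregation induced through the thromboxane prostanoid receptor, and this trial gives 200 mg daily. Section 5.5 names bleeding through impaired platelet function as a potential risk. Exclusion 7 keeps out subjects on antiplatelet or anticoagulant drugs, so the protocol already avoids adding ifetroban to weakened hemostasis. A very low platelet count belongs to the same concern and is not listed.

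At stake is the safety of a rare subject, and whether all eight planned centers would decide about that subject in the same way.

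**Working it through.** Apart from a few counts this is a text check. The one figure it turns on, < 50 × 10⁹/L, is read directly from section 9.1.

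**1. Count the entry limits in section 7.4.**
- Entry criteria: 6 inclusion + 12 exclusion = 18.
- Numeric limits on a screening measurement other than a blood result: 2 (FEV1 ≥ 60% in inclusion 4; SNOT-22 ≥ 20 in inclusion 6).
- Numeric limits on a blood result: 0. Exclusion 2 (pregnancy) can rest on a serum test but sets no blood-count limit.

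The criteria in the synopsis and in SAP 4.2 contain no platelet limit either.

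**2. Ask whether any criterion reaches the subject indirectly.** Take a subject with a screening count below 50 × 10⁹/L, no known bleeding history and no recent antiplatelet or anticoagulant drug.
- Exclusion 7 looks to history and drugs, so it does not clearly apply to a low count first found at Screening.
- Exclusion 12 does not apply, because SNOT-22 can still be evaluated.
- There is no general safety exclusion at the investigator's discretion.

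**3. Follow that subject through Week 0.** Section 8.1.2 treats unmet entry criteria as the ground for screen failure and sends everyone who satisfies the list on to randomization. This subject satisfies it.

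**4. Compare entry with the withdrawal list in 9.1.**

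| Item in 9.1 | Counterpart at entry |
|---|---|
| Platelets < 50 × 10⁹/L | None, although the count is measured at Screening |
| Pregnancy (appears to close the list) | Exclusion 2 |
| Hemoglobin drop of at least 10% from baseline | Cannot be met at entry |
| Serious arrhythmia, gastrointestinal bleeding, related serious adverse event | Events, not screening values |

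Platelets are the only item that is both a fixed level and already measured before dosing.

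**5. Look for a later check.** Hematology in Table 8–1:
- Screening: yes.
- Week 0: waived if the screening labs fall within three weeks of first dose. Section 8.1 requires screening to fit that window, so the waiver should normally apply.
- Week 1 and Week 4: none.
- Week 8: yes. 8 × 7 = day 56, or days 51 to 61 with the ± 5 day window.
- Week 10: only if abnormal at Week 8.

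The screening count is therefore normally the only one before dosing. If blood is drawn at Week 0, the draw is listed after randomization. It must precede dosing, but nothing requires the result to be back first.

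**The case against.** The strongest reply is that the protocol already has ways to stop this subject.

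- **Laboratory results already bear on eligibility.** Section 8.1.1 places the blood samples among the procedures that determine eligibility, and 8.1.2 has eligibility reconfirmed before randomization. The rescreening rule in 8.1 begins "Subjects that fail screening for exclusion criteria, for example concomitant medications, acute illness (upper respiratory tract infection" and goes on to name laboratory tests. This shows that the drafters expected a laboratory result to be able to fail a subject. But the sentence ties failure to the exclusion criteria, and apart from pregnancy none of them contains a laboratory test. The step is there; the limit is not.
- **Section 9.1 might apply from Screening onward.** Screening is one of the three study periods, and the rule is not restricted to treatment. That reading is possible, but the rule concerns events that occur, so its force at entry is ambiguous. Applying it after randomization would lose a subject, and 9.1 does not replace early terminations.
- **A careful investigator would decline.** Probably so, but the protocol does not require it.
- **Other withdrawal items have no entry counterpart.** True of arrhythmia and gastrointestinal bleeding, but those are events rather than a value already in hand at Screening.
- **A cut-off of 50 would still admit a count of 51.** This stands. The documents support no particular higher value, so a stricter limit is a medical decision.

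It also stands that no section says ifetroban lowers platelet counts, that 5.5 reports neither bleeding events nor abnormal laboratory findings in Phase 2a, and that there are other safeguards: the Week 1 call, adverse-event review at Week 4, the remaining withdrawal rules and an Independent Safety Monitor. These limit the importance of the gap without closing it.

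**Conclusion.** The concern holds, as a minor safety point. Followed literally, the entry rule lets a subject whose screening count is already below the protocol's own withdrawal level be randomized and dosed. High confidence attaches to the omission; its practical weight is small.

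- **Size:** such subjects should be very rare. The documents give no frequency and none is assumed. The interval to the Week 8 count is context only.
- **Effect on inference:** none on sample size, power or the analysis.
- **What it rests on:** that the list in 7.4 decides eligibility, as 7.4, 8.1.1 and 8.1.2 say, and that a low count without a bleeding history is not itself read as a history of bleeding diathesis.

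**What to change.** 1. Add to the synopsis exclusion list and to section 7.4.2: *Screening platelet count < 50 × 10⁹/L*. This matches 9.1; the sponsor's medical team may set a stricter limit.
2. In section 8.1.1, and in the Week 0 list of 8.1.2 ahead of the randomization step, require review of the screening hematology result.

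No PT or INR limit is proposed, and no SAP analysis changes.

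The cost is one exclusion line in two places and one review line in two visit lists. The sample is already drawn. The downsides are a rare extra screen failure and the need to have the result back before Week 0. The change does not bring forward the next count for enrolled subjects; it only keeps out those already below the limit.

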# Investigational Medicinal Product (IMP), dose and mode of administration:

Oral ifetroban capsules (200 mg)

# **Duration of treatment:** eight weeks

Name of Sponsor:	Name of Finished Product:	Name of Active Ingredient:			
Cumberland Pharmaceuticals	Ifetroban Capsules	ifetroban			
Reference therapy, dose and mode of administration:					
Matching oral placebo capsules					
Enducintes					

#### **Endpoints:**

Efficacy: SNOT-22, ACQ-7, FEV1, UPSIT, FeNO, PNIFR and TNSS

**Safety, tolerability and other exploratory endpoints:** vital signs, adverse events (AE), physical examination, clinical laboratory tests and biomarkers.

# Sample Size:

38 subjects per group will provide 90% power for the comparison of ifetroban and placebo with respect to the change from baseline in SNOT-22 scores at Week 8 (two-sided, level 0.05), assuming a common standard deviation of 16 and a true difference is 12.

#### **Randomization:**

Subjects will be randomized using a 1:1 randomization ratio for ifetroban 200 mg daily for eight weeks, or placebo daily for eight weeks.

#### **Analysis Population:**

All subjects who received at least one dose of study medication will be included in the Safety Population. All safety data, including AEs, laboratory parameter, vital signs, FEV1 and physical examinations, will be summarized for subjects in the Safety Population.

The Intent-To-Treat (ITT) Population will consist of all treated subjects with at least one post-baseline assessment of SNOT-22. The Per Protocol (PP) Population will consist of all subjects in the ITT population with no major protocol violations, including violation of inclusion or exclusion criteria or insufficient dosing. All efficacy analyses will be performed for both the ITT and PP Populations. Summary statistics will be presented for each corresponding analysis.

#### **Primary Analysis:**

The primary efficacy endpoint is the Change From Baseline (CFB) in SNOT-22 score and the primary analysis is the analysis of CFB in SNOT-22 at Week 8, using Analysis of Covariance (ANCOVA), with SNOT-22 at Baseline included as the only covariate.

#### **Secondary Analyses**

CFB in ACQ-7 and CFB in TNSS at Week 8 will be analyzed using ANCOVA, with the corresponding value at Baseline included as the only covariate. These variables, as well as CFB in SNOT-22, at Week 4 will also be analyzed as ancillary analyses.

Analyses of CFB for other continuous efficacy variables at Weeks 4 and 8 will be performed as ancillary analyses using ANCOVA with the corresponding value at Baseline included as the only covariate. Responder analyses, defined as any improvement in SNOT-22, ACQ-7, and TNSS (Yes or No) at Weeks 4 and 8 will be performed as ancillary analyses using the normal approximation to the binomial distribution, assuming unequal variances.

# 4 LIST OF ABBREVIATIONS

. 210	
Abbreviation	Definition
5-LO	5-Lipoxygenase
ACQ	Asthma Control Questionnaire
AE	Adverse Event/Experience
AERD	Aspirin Exacerbated Respiratory Disease
ANCOVA	Analysis of Covariance
AUC	Area Under the Curve
C	Celsius
CFB	Change From Baseline
CFR	Code of Federal Regulations
cm	Centimeter
$C_{\text{max}}$	Maximum Plasma Concentration
COX	Cyclooxygenase
CRF	Case Report Form
CPI	Cumberland Pharmaceuticals Inc.
cysLT	Cysteinyl Leukotriene
CysLT1R	Cysteinyl Leukotriene 1 Receptor
ER	Emergency Room
F	Fahrenheit
FDA	Food and Drug Administration
FeNO	Fractional exhaled Nitric Oxide
FEV1	Forced Expiratory Volume in 1 Second
GCP	Good Clinical Practice
ICH	International Conference on Harmonization
IEC	Independent Ethics Committee
IMP	Investigational Medicinal Product; synonymous with "study drug"
INR	International normalized ratio
IRB	Institutional Review Board
ITT	Intent-To-Treat
kg	Kilogram
L	Liter
$LTC_4$	Leukotriene C 4
LTE 4	Leukotriene E 4

Minimal Clinically Important Difference

Medical Dictionary for Regulatory Activities

